3.3 Exclusion Criteria

- 3.31 Medical contraindication to receipt of radiotherapy.
- 3.32 Severe active co-morbid systemic illnesses or other severe concurrent disease which, in the judgment of the investigator, would make the patient inappropriate for entry into this study or interfere significantly with the proper assessment of safety and toxicity of the prescribed regimens.
- 3.33 Uncontrolled intercurrent illness including, but not limited to, ongoing or active infection, symptomatic congestive heart failure, unstable angina pectoris, cardiac arrhythmia, or psychiatric illness/social situations that would limit compliance with study requirements or providing informed consent.
- 3.34 Active systemic lupus or scleroderma.
- 3.35 Women of childbearing potential who are sexually active and not willing/able to use medically acceptable forms of contraception.
- 3.36 Prior receipt of ipsilateral breast or chest wall radiation.
- 3.37 Positive margins on ink after definitive surgery either for DCIS or invasive cancer.
- 3.38 History of non-breast malignancies (except for in situ cancers treated only by local excision and basal cell and squamous cell carcinomas of the skin) within 5 years prior study entry.
- 3.39 Recurrent breast cancer.
- 3.40 Indications for comprehensive regional nodal irradiation.
- 3.41 Male subjects.
- 3.42 Patient requires bilateral breast radiation treatment.

4.0 Test Schedule

	Baseline	Pre-treatment	EOT	Observation ¹²			
	≤120 days prior to start of treatment	≤45 days prior to start of treatment ⁶	Last day of Treatment (+/- 5 days)	12 weeks (+/- 4 weeks) post-treatment	6 months (+/- 2 months)	12 months (+/- 3 months), 24 months (+/- 6 months), 36 months (+/- 6 months), 48 months (+/- 6 months) and 5 years (+/- 6 months) post completion of treatment	Failure*
Consent	X						
Physical exam ¹	X						
Exam/ECOG							
Visit (see Appendix)	X		X ⁸	X		X	X
Visit (see Section)		X ⁹	X ⁸	X		X ¹³	X
Visit ³		X	X	X		X	
Visit (sites 2,3,4) ¹¹		X ⁹	X	X	X	X	X
Visit (see)		X ⁹	X	X		X	X
Specimens							
Initial specimen	X ⁵						X ²
							X ⁷

1. A general history & physical exam should include height and weight (optional at Rochester site)
2. Review of pathology at failure if obtained clinically
3. Photographs can be done at any time before or after treatment at the discretion of the physician
4. Last day of treatment +/- 2 days per discretion of treating physician
5. Outside pathology must be reviewed at treating institution to confirm eligibility within 365 days.
6. Blood pregnancy test to be completed prior to start of treatment on day 1 (for women of childbearing potential only).
7. PET Scan at failure optional
8. Per discretion of treating physician for Arm 2 (5 days)
9. These tests can be done before or up to 3 days into treatment
10. Limited physical exam to include ECOG; weight (optional for Rochester site)
11. As collected clinically
12. Patients that cannot come back to Mayo within the time constraints of the follow-up schedule; efforts to obtain outside records and complete QOL's will occur, however the required items may not be captured.
13. If follow up visit occurred at an outside institution, Cosmetic Assessment will not be required.

*Failure defined as recurrent disease

5.0 Stratification Factors

- 5.1 Treatment modality: Photons vs. spot scanned proton therapy. Of the total 110 patients in this study, fifty-five would be treated in each arm. We will

allow a maximum of 28 patients per arm per treatment modality (photons/x-ray or protons).

6.0 Registration / Randomization Procedures

6.1 Registration Procedures

6.1 Patient will be registered to the study when they have consented, met eligibility criteria, and have been logged into Research Participant Tracking (Ptrax).

6.2 Screening tests/procedures (see section 4.0) will be completed within the guidelines specified on the assessment schedule.

6.2 Randomization Procedures

6.21 The factors defined in Section 5.0, together with the registering membership, will be used as stratification factors.

6.22 After the patient has been registered into the study, the values of the stratification factors will be recorded, and the patient will be assigned to one of the following treatment groups using the Pocock and Simon dynamic allocation procedure which balances the marginal distributions of the stratification factors between the treatment groups.⁵⁷

7.0 Protocol Treatment

Doses throughout will be prescribed in Gy (RBE) / Gy or Gy. One Gy will be the equivalent of one Gy (RBE) / Gy for proton therapy for the purposes of the descriptions below. Radiation therapy must begin within 12 weeks of the last breast cancer surgery or the last dose of adjuvant chemotherapy and no sooner than 14 days since the last chemotherapy. The dose, schedule, and timing (neoadjuvant vs adjuvant) of chemotherapy and endocrine therapy are at the discretion of the treating oncologists. Concurrent cytotoxic chemotherapy with radiotherapy is not allowed. Use of anti-HER2 therapy during radiotherapy is permitted.

The treatment technique (photon/x-ray vs. proton) utilized will be at the physician's discretion and will be based on technical considerations, availability at the radiation oncology facility, insurance coverage considerations, and patient preference. See section 7.4.

7.1 Radiation Therapy, Arm 1

Patients who had breast conserving surgery and are randomized to arm 1 (standard fractionation) will receive whole breast radiotherapy delivered to the breast CTV with or without a sequential boost to the lumpectomy cavity CTV. Boost indications will be left to physician discretion. Potential risk factors suggesting increased absolute benefit from a boost include but are not limited to age < 40, close margins, extensive DCIS adjacent to the invasive tumor.^{58,59}

7.2 Radiation Therapy, Arm 2

Patients who had breast conserving surgery and are randomized to arm 2 (5 fraction hypofractionation) will receive whole breast radiotherapy in 5 daily fractions delivered to the breast CTV with or without a concurrent boost to the lumpectomy cavity CTV. Boost indications will be left to physician discretion. Potential risk factors suggesting increased absolute benefit from a boost include but are not limited to age < 40, close margins, extensive DCIS adjacent to the invasive tumor.^{58,59}

7.3

Dose Specifications

7.31 Arm 1 Post-lumpectomy whole breast irradiation +/- sequential boost

7.311 Breast: 40.05Gy (RBE) / Gy/Gy in 15 fractions of 2.67 Gy (RBE) / Gy/Gy

7.312 Lumpectomy cavity (optional): Sequential boost dose will be 10 Gy (RBE) / Gy in 2.5 Gy (RBE) / Gy fractions for a total dose of 50.05Gy (RBE) / Gy / Gy. Simultaneously integrated boost is allowed to a total dose of 48Gy (RBE) / Gy over 15 fractions.

7.32 Arm 2 Post-lumpectomy whole breast irradiation +/- concurrent boost

7.321 Breast: 25 Gy (RBE) / Gy in 5 fractions of 5 Gy (RBE) / Gy

7.322 Lumpectomy cavity (optional): Dose to the lumpectomy cavity (concurrent boost dose) will be 30 Gy (RBE) / Gy in 5 fractions of 6 Gy (RBE) / Gy

7.4

Treatment Technique

7.41 Radiation will be delivered using available photon (x-ray) or scanning beam proton equipment at the treating institution.

7.42 Only one breast will be treated on the protocol.

7.43 While planning the scanning target volumes, care must be taken to not put Bragg Peaks either in the Chest Wall or in the first 5 mm from the external surface of the body.

7.5

Localization, Simulation, Immobilization

7.51 Simulation should be performed with the patient in the supine or prone position

7.52 Patients should be optimally positioned with a custom immobilization device at the discretion of the treating physician.

7.53 Arm position may be up or down.

7.54 The CT should extend cephalad to at least the level of the mandible to include both elbows and extend caudally to encompass the entire lung volume. The CT scan thickness will be 2mm.

7.55 External skin markers, which may include permanent tattoos, are recommended for daily set-up.

7.56 KV image guidance will be performed daily. Other imaging modalities, such as CBCT and Vision RT, real time tracking or others should be performed based on institutional guidelines.

7.57 Volumetric imaging may be performed with re-planning at the physician's discretion.

7.6

Treatment Planning

7.61 For proton planning, 1 or more en face or oblique fields are recommended.

7.7 Target Volumes

The definitions for the CTV and normal structures for this protocol will generally follow the RTOG (Radiation Therapy Oncologic Group)-endorsed consensus guidelines for delineation for breast cancer [REDACTED] with exceptions described below.

7.71 Post-lumpectomy breast target volumes (Arms 1 and 2)

7.711 **High tangents volume:** Alternatively, breast target volume can be defined by traditionally treated volume. All palpable breast tissue and all tissue encompassed by a standard tangent fields would be considered breast tissue. A medial tangent would be placed at the costo-condral junction and a lateral tangent would be placed at the mid axillary line or more posterior as necessary to cover all breast tissue laterally. The caudal border would be 1 cm below all breast tissue. The superior border would be placed at the second intercostal space. Position would be verified on CT and in general it should not be closer than 1.5 cm from the inferior border of the humeral head and no more than 2 cm distally.

7.712 **Low tangents volume:** would be defined in the same manner; with the exception that the superior border should be between 2-4 cm from the inferior border of the humeral head.

7.713 **Manual modifications:** alternatively, volumes can be defined using the RTOG breast atlas as above. However, for uniformity of the posterior margin the breast volume would include muscle tissue as needed to maintain a uniform distal edge. Please see breast CTV (section 7.7.1.4.2).

7.714 Lumpectomy Cavity: Contour using the excision cavity volume, architectural distortion, lumpectomy scar, seroma and/or extent of surgical clips (clips and/or fiducials are strongly recommended).

7.7.1.4.1 **Lumpectomy Cavity CTV:** Lumpectomy Cavity + 5mm 3 D expansion. Limit the CTV 5 mm from skin.

7.7.1.4.2 Breast CTV: the breast would be the same as the CTV high tangents or low tangents without further expansions. The lumpectomy CTV is also included. The breast CTV volume is limited 5mm from the skin. The breast CTV posteriorly, would be limited 5mm from the lung excluding the chest wall.

7.715 Photon therapy

7.7.1.5.1 **PTV-eval (PTV evaluation):** PTV evaluation would be used for photon patients. PTV eval would equal to the breast CTV as defined above. The breast CTV as defined above matches the definition of the RTOG 1005 "This Breast PTV Eval is limited anteriorly to exclude the part outside the patient and the first 5 mm of tissue under the skin (in order to remove most of the buildup region for the DVH analysis) and posteriorly is limited no deeper to the anterior surface of the ribs (excludes boney thorax and lung)."

7.8

Critical Structures

7.81 **Breast skin eval:** Will be defined as the first 3 mm of tissue under the body surface anterior to the Breast CTV.

7.82 **Heart:** To be contoured on all cases. The contour should begin just inferior to the level in which the pulmonary trunk branches into the left and right pulmonary arteries (PA) and should extend to its most inferior extent near the diaphragm. The esophagus, ascending and descending aorta and inferior vena cava should be excluded from the heart contour.

7.83 **Left anterior descending (LAD) interventricular branch:** To be contoured on left sided cases. “Originates from the left coronary artery and runs in the interventricular groove between the right and left ventricles. If it is difficult to see, raising the level and lowering the window may help (e.g. level 50, window 150)”.⁶⁰

7.84 **Right coronary artery (RCA).** To be contoured on all right-sided cases. “Originates from the right side of the ascending aorta. Due to the native heart position in the chest, on axilla CT, it appears to start inferior to the left coronary artery. It moves significantly with cardiac motion, so often the location can seem noncontiguous from axial CT slice to slice, as the position of the AV groove changes.”⁶⁰

7.85 **Ipsilateral lung:** To be contoured on all cases, auto-segmentation with manual verification is permitted

7.86 **Contralateral lung:** To be contoured on all cases, auto-segmentation with manual verification is permitted

7.87 **Total lung:** To be contoured on all cases, auto-segmentation with manual verification is permitted

7.88 **Contralateral breast:** Dose to the contralateral breast will not be constrained in treatment planning and therefore contouring of the contralateral breast is not required in this protocol. However, efforts should be made to limit inadvertent dosing of the contralateral breast.

7.89 **Chest wall:** from patient’s midline, at the mid plane of the sternum, to the patient’s posterior axillary line. The thickness would be defined by measuring the distance from the lung-chest wall interface to the posterior edge of the pectoralis muscle and creating virtual structure. It can be manually modified to exclude the pectoralis muscle at the discretion of the treating physician. No breast tissue should be included in this structure. The CTV should not be included in this structure plus 2mm.

7.9 **Prescription and Normal Tissue Constraints**

7.91 **Arms 1 and 2 (protons and photons/x-rays)**
7.911 Breast CTV:

7.9.1.1.1 Per protocol \geq D95% will receive \geq 95% of prescription;
Variation acceptable \geq D90% receives \geq 90% of prescription

7.912 Tumor CTV

7.9.1.2.1 Per protocol D95% receives \geq 95% of dose; variation acceptable D90% receives \geq 90% of the boost dose

7.913 Robustness analysis **for Protons**

7.9.1.3.1 Breast CTV coverage would be evaluated for 5mm movements or 3% range changes. Per protocol Breast CTV V90% receives \geq 95% of the prescription dose; variation acceptable \geq V90% receives \geq 90% of the prescription dose.

7.9.1.3.2 Under the same robustness evaluation criteria, plans will be evaluated for D max. Variation acceptable D0.01cc % \leq 120%

Protons DVH summary table

		Goal	Major violation ¹
Breast CTV		\geq V95% will receive \geq 95% of prescription	V90% $<$ 90% of prescription
		Dmax $<$ 107%	Dmax $>$ 115%
Tumor Bed CTV		\geq V95% will receive \geq 95% of prescription	V90% $<$ 90% of prescription
		Dmax $<$ 107%	Dmax $>$ 115%
Breast CTV robustness		V90% $>$ 90% of prescription	V90% $<$ 90% of prescription
Heart	Max dose	\leq 25% of prescription	$>$ 33% of prescription
	Mean	$<$ 0.1Gy	$>$ 1Gy
Breast Skin	Max dose	\leq 105% of prescription	$>$ 110% of prescription
Lung Ipsilateral	V50% of prescription	\leq 10%	$>$ 15%
	V20	record	
Lung contralateral	V50%	\leq 7%	$>$ 10%
Lung Total	Mean dose	record	
	V20Gy	record	
	V50%	record	
LAD (optional)	Mean dose	record	
	Max dose	record	
RCA (optional)	Mean dose	record	
	Max dose	record	

1. Major violations do not exclude patients from the protocol as it is an intent to treat analysis

Photons (x-rays) DVH summary table

		Goal	Major violation
PTV Eval		\geq V95% will receive \geq 95% of prescription	V90% <90% of prescription
		Dmax <107%	Dmax >115%
Tumor Bed CTV		\geq V95% will receive \geq 95% of prescription	V90% <90% of prescription
		Dmax <107%	Dmax >115%
Breast CTV robustness		V90% >90% of prescription	V90% <90% of prescription
Heart	Max dose	\leq 33% of prescription	>50% of prescription
	Mean	<1Gy	>2Gy
Breast Skin	Max dose	\leq 107% of prescription	>115% of prescription
Lung Ipsilateral	V50% of prescription	\leq 10%	>15%
	V20	record	
Lung contralateral	V50%	\leq 7%	>10%
Lung Total	Mean dose	record	
	V20Gy	record	
	V50%	record	
LAD (optional)	Mean dose	record	
	Max dose	record	
RCA (optional)	Mean dose	record	
	Max dose	record	

1. Major violations do not exclude patients from the protocol as it is an intent to treat analysis

Quality Assurance Documentation

7.92 At a minimum, the initial 2 treatment plans per institution will be centrally reviewed by the principal investigator or designee prior to the start of treatment.

8.0 Radiotherapy Dose Modifications Based on Adverse Events

This study has no pre-specified interruptions due to adverse events. Treatment interruptions are discouraged. No dose modifications should be done for treatment interruptions.

9.0 Ancillary Treatment/Supportive Care

Skin changes are common complications of breast cancer radiation therapy. Usual care will be

provided as per the treating institution's standard of practice. If the skin becomes erythematous and/or there is pruritus, topical steroid cream may be prescribed. The addition of antihistamines may be used for severe pruritus. Patients experiencing pain will be prescribed pain medication.

10.0 Adverse Event (AE) Reporting and Monitoring

10.1 Definitions

Adverse Event- An untoward or undesirable experience associated with the use of a medical product (i.e. drug, device, biologic) in a patient or research subject.

Serious Adverse Event – Any grade 4 or 5 adverse event as defined by CTC AE v4.0.

Adverse events are classified as serious or non-serious. Serious problems/events can be well defined and include in general:

- Death
- Life threatening adverse experience where emergent lifesaving treatment is necessary.

Unanticipated Problems Involving Risks to Subjects or Others (UPIRTSO) - Any unanticipated problem or adverse event that meets the following three criteria:

Serious: Serious problems or events that results in significant harm, (which may be physical, psychological, financial, social, economic, or legal) or increased risk for the subject or others (including individuals who are not research subjects). These include: (1) death; (2) life threatening adverse experience; (3) hospitalization - inpatient, new, or prolonged; (4) disability/incapacity - persistent or significant; (5) birth defect/anomaly; (6) breach of confidentiality and (7) other problems, events, or new information (i.e. publications, DSMB reports, interim findings, product labeling change) that in the opinion of the local investigator may adversely affect the rights, safety, or welfare of the subjects or others, or substantially compromise the research data, **AND**

Unanticipated: (i.e. unexpected) problems or events are those that are not already described as potential risks in the protocol, consent document, not listed in the Investigator's Brochure, or not part of an underlying disease. A problem or event is "unanticipated" when it was unforeseeable at the time of its occurrence. A problem or event is "unanticipated" when it occurs at an increased frequency or at an increased severity than expected, **AND**

Related: A problem or event is "related" if it is possibly related to the research procedures.

Preexisting Condition- A preexisting condition is one that is present at the start of the study. A preexisting condition should be recorded as an adverse event if the frequency, intensity, or the character of the condition worsens during the study period. At screening, any clinically significant abnormality should be recorded as a preexisting condition. At the end of the study, any new clinically significant findings/abnormalities that meet the definition of an adverse event must also be recorded and documented as an adverse event.

10.2 Recording Adverse Events

CTCAE term (AE description) and grade: The descriptions and grading scales found in the revised NCI Common Terminology Criteria for Adverse Events (CTCAE) version 4.0 will be utilized for AE reporting unless as otherwise stated in the table below.

All appropriate treatment areas should have access to a copy of the CTCAE version 4.0. A copy of the CTCAE version 4.0 can be downloaded from the CTEP web site: (http://ctep.cancer.gov/protocolDevelopment/electronic_applications/ctc.htm)

10.21 Adverse event monitoring and reporting is a routine part of every clinical trial. First, identify and grade the severity of the event using the CTCAE version 4.0. Next, determine whether the event is expected or unexpected and if the adverse event is related to the medical treatment or procedure. With this information, determine whether the event must be reported as an expedited report (see Section 10.3).

10.22 Assessment of Attribution

Only G4 or G5 adverse events will require an attribution. Any change in the grade of an adverse event within the list of monitored AEs will be recorded and considered to be related to treatment. Any new adverse not listed occurring within the Radiated area or in close proximity will be graded and attribution defined by the study PI.

Events determined to be possibly, probably or definitely attributed to a medical treatment suggest there is evidence to indicate a causal relationship between the treatment and the adverse event.

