10.3 Reporting of Serious Adverse Events and Unanticipated Problems

When an adverse event has been identified, the study team will take appropriated action necessary to protect the study participant and then complete the Study Adverse Event Worksheet and log. The sponsor-investigator will evaluate the event and determine the necessary follow-up and reporting required.

- a. Serious Adverse Events will be reported as part of regular adverse event reporting mechanisms via the data capture system and logged for review reporting.

10.31 Investigator Reporting: Notifying the Mayo IRB:

The IRB requirements reflect the guidance documents released by the Office of Human Research Protections (OHRP), and the Food and Drug Administration (FDA) in early 2007 and are respectively entitled “Guidance on Reviewing and Reporting Unanticipated Problems Involving Risks to Subjects or Others and Adverse Events” and “Guidance for Clinical Investigators, Sponsors, and IRBs: Adverse Event Reporting – Improving Human Subject Protection.”

10.311 According to Mayo IRB Policy any serious adverse event (SAE) which the Principal Investigator has determined to be a UPIRTSO must be reported to the Mayo IRB as soon as possible but no later than 5 working days after the investigator first learns of the problem/event.

10.312 Non-UPIRTSO – the investigator reports problems or events that do NOT meet criteria of an UPIRTSO in summary format at the

time of the next continuing review. The investigator monitors the severity and frequency of subsequent non-UPIRTSOs.

Consider the following information to collect when developing any forms for documentation of adverse events.

Example

Information collected on the adverse event worksheet (and entered in the research database):

- Subject's name:
- Medical record number:
- Disease/histology (if applicable):
- The date the adverse event occurred:
- Description of the adverse event:
- Relationship of the adverse event to the research (drug, procedure, or intervention):
- If the adverse event was expected:
- The severity of the adverse event: (use a table to define severity scale 1-5)
- If any intervention was necessary:
- Resolution: (was the incident resolved spontaneously, or after discontinuing treatment)
- Date of Resolution:

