The investigator will review all adverse event reports to determine if specific reports need to be made to the IRB and FDA. The investigator will sign and date the adverse event report when it is reviewed. For this protocol, only directly related SAEs/UPIRTSOs will be reported to the IRB.

10.4 Adverse events to be graded at each evaluation and pretreatment symptoms/conditions to be evaluated at baseline per the CTCAE v5.0 grading unless otherwise stated in the table below. Version 4 is allowed if v5 is not available, however, AEs will have to be updated to V5 once is available:

System (SOC)	Organ Class	Adverse event/Symptoms	Baseline	Each evaluation	Grading scale (if not CTCAE)
General		Pain	X	X	CTCAE
Skin and subcutaneous tissue disorders		Dermatitis Radiation	X	X	CTCAE
		Skin hyperpigmentation	X	X	CTCAE
		Skin hypopigmentation	X	X	CTCAE
		Superficial Soft Tissue Fibrosis	X	X	CTCAE
		Breast edema (lymphedema)	X	X	CTCAE

Vascular	Lympedema -arms	X	X	CTCAE
Respiratory, thoracic and mediastinal disorders	Pneumonitis	X	X	CTCAE

10.5 Submit via appropriate *reporting mechanisms* the following AEs experienced by a patient and not specified in Section 10.4:

- 10.52 Grade 3, 4, and 5 AEs regardless of attribution to the study treatment or procedure.
- 10.53 Grade 5 AEs (Death)
- 10.531 Any death within 30 days of the patient's last study treatment or procedure regardless of attribution to the study treatment or procedure
- 10.532 Any death more than 30 days after the patients last study treatment or procedure that is felt to be at least possibly treatment related must also be submitted as a Grade 5 AE, with a CTCAE type and attribution assigned.

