16.62 Secondary Analyses

16.621 *Acute adverse events:* All patients who were registered to the study and started treatment will be included in the acute adverse event analysis. An acute adverse event is an AE, regardless of attribution, that occurs up to 90 days post-RT. The maximum grade for each type of acute AE will be recorded for each patient. Data will be summarized as frequencies and relative frequencies by treatment arm. Additionally, the relationship of the adverse event(s) to the study treatment will be taken into consideration. Rates will be compared between arms using chi-squared tests.

16.622 *Late adverse events:* All patients who were registered to the study and started treatment will be included in the late adverse event analysis. A late adverse event is an AE, regardless of attribution, that appears or persists after 90 days post-RT and up to 5 years post-RT. The maximum grade for each type of late AE will be recorded for each patient. Data will be summarized as frequencies and relative frequencies by treatment arm. Additionally, the relationship of the adverse event(s) to the study treatment will be taken into consideration. Rates will be compared between arms using chi-squared tests.

16.623 *Locoregional control:* The cumulative incidence of locoregional recurrence will be estimated using a competing risks method (Gooley et al.) by treatment arm. The competing risks will be distant breast cancer recurrence and death. Comparison between arms will employ Fine-Gray regression.

16.624 *Invasive disease-free survival:* i-DFS is defined as the time from registration until the time of invasive disease recurrence (not including DCIS) or death due to any cause. The i-DFS will be estimated with a Kaplan-Meier estimator and curve by treatment arm. Estimates will be given for specific time points along with 95% CIs. Comparison between arms will employ a log-rank test.

16.625 *Disease-free survival:* DFS is defined as the time from registration until the time of disease recurrence or death due to any cause. The DFS will be estimated with a Kaplan-Meier estimator and curve by treatment arm. Estimates will be given for specific time points along with 95% CIs. Comparison between arms will employ a log-rank test.

16.626 *Cause specific survival:* The CSS will be estimated with a Kaplan-Meier estimator and curve by treatment arm. Estimates will be given for specific time

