16.7 Data & Safety Monitoring

16.71 The study chair(s) and the study statistician will review the study at least twice a year to identify accrual, adverse event, and any endpoint problems that might be developing. The Mayo Clinic Cancer Center (MCCC) Data Safety Monitoring Board (DSMB) is responsible for reviewing accrual and safety data for this trial at least twice a year, based on reports provided by the MCCC Statistical Office.

16.72 Adverse Event Stopping Rules: The stopping rules specified below are based on knowledge available at study development. We note that the Adverse Event Stopping Rule may be adjusted in the event of either (1) the study re-opening to accrual or (2) at any time during the conduct of the trial and in consideration of newly acquired information regarding the adverse event profile of the treatment(s) under investigation. The study team may choose to suspend accrual because of unexpected adverse event profiles that have not crossed the specified rule below.

Accrual will be temporarily suspended if at any time we observe events considered at least possibly related to study treatment (i.e. an adverse event with attribute specified as “possible,” “probable,” or “definite”) that satisfy one of the following:

- If 4 or more patients in the first 10 treated patients (per treatment arm) experience a grade 3 or higher adverse event, besides acute dermatitis, at least possibly related to treatment at any time following completion of the protocol treatment within 90 days post-treatment.
- After the first 10 patients have been treated (per treatment arm): if $\geq 20\%$ of all patients experience a grade 3 or higher adverse event, besides acute

dermatitis, at least possibly related to treatment at any time following the completion of protocol treatment within 90 days post-treatment.

We note that we will review grade 4 and 5 adverse events deemed “unrelated” or “unlikely to be related”, to verify their attribution and to monitor the emergence of a previously unrecognized treatment-related adverse event.

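### Section 10.22 does not require attribution for unlisted grade 3 events away from the irradiated area, so the accrual-suspension rule in 16.72 may miss them

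*Combined protocol and SAP*

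**What the plan says.** Section 10.22 opens with "Only G4 or G5 adverse events will require an attribution". It then gives two provisions with no grade limit:

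- A change in grade of an event "within the list of monitored AEs will be recorded and considered to be related to treatment". The list is the table in 10.4.
- "Any new adverse not listed occurring within the Radiated area or in close proximity will be graded and attribution defined by the study PI".

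Section 10.21, on recording events in general, tells staff to grade the event and then to "determine whether the event is expected or unexpected and if the adverse event is related to the medical treatment or procedure". It names no grade threshold. The example worksheet in 10.3 includes "Relationship of the adverse event to the research (drug, procedure, or intervention" among the items to consider collecting. Section 10.52 calls for submission of unlisted "Grade 3, 4, and 5 AEs regardless of attribution to the study treatment or procedure".

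Section 16.72 says: "Accrual will be temporarily suspended if at any time we observe events considered at least possibly related to study treatment". It defines these as events attributed as possible, probable or definite. The grade condition is 3 or higher, acute dermatitis excepted, within 90 days after treatment. The trigger is four of the first ten patients treated in an arm, and after that 20% or more. A further review of attribution is promised only for grade 4 and 5 events judged unrelated or unlikely to be related.

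For the acute and late adverse event analyses, 16.621 and 16.622 add: "Additionally, the relationship of the adverse event(s) to the study treatment will be taken into consideration".

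**The concern.** The suspension rule selects grade 3 events by their attribution, and the section that governs attribution does not require one at grade 3. Where neither provision of 10.22 supplies a relationship, a grade 3 event can be on file with no attribution and so fall outside the count. Sites that follow 10.21 would record relatedness for such an event; sites that follow 10.22 need not. The same event could then count at one site and not at another.

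At stake is whether a pre-specified safety trigger can be applied consistently. An unattributed event can only lower the count, never raise it, so any error is towards not suspending.

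**Working it through.** The documents give no operating characteristics for the suspension rule, so there is no stated figure to reproduce. The main check is a comparison of the sections.

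**Step 1. Which grade 3 events have a relationship under 10.22?**

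| Grade 3 event | Relationship under 10.22 | Usable by 16.72? |
|---|---|---|
| On the 10.4 list | Deemed related when the grade changes | Yes in intent, but no text equates deemed related with possible, probable or definite |
| Unlisted, in or near the irradiated area | Assigned by the study PI | Yes |
| Unlisted, elsewhere | None required | Only if someone records it under 10.21 |

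**Step 2. Does another provision close the third row?**

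- 10.21 asks for relatedness at any grade, but 10.22 is the specific section and restricts the requirement with the word only. The two conflict.
- The worksheet in 10.3 is offered as an example, so it does not bind.
- 10.52 brings the event in, but whatever its attribution. Submission does not supply the missing value.
- The back-up review in 16.72 stops at grades 4 and 5.

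**Step 3. Is the third row empty in practice?** The 10.4 list has eight items: pain, radiation dermatitis, hyperpigmentation, hypopigmentation, superficial soft tissue fibrosis, breast edema, arm lymphedema and pneumonitis. Fatigue is not on it and does not arise in the irradiated area. Section 1.2 reports one case of grade 3 fatigue during treatment in a cited post-mastectomy proton cohort of 12 patients, with no skin toxicity of grade 3 or above. Section 2.31 names fatigue as an outcome of interest. The class is therefore real, though to reach the rule such an event must also be at least possibly related and fall within the rule's time window.

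**Step 4. Direction and possible size (assumed values only).** Let p be the true proportion of patients with a qualifying related grade 3 or higher event, and c the share of those patients whose event carries an attribution. Neither is in the documents. Assume at most one qualifying event per patient and independent patients. The number counted among the first ten in an arm is then binomial with probability p × c, and

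P(suspend) = 1 − Σ (k = 0 to 3) C(10, k) (pc)^k (1 − pc)^(10 − k).

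For p = 30% and c = 100%: 1 − (0.0282 + 0.1211 + 0.2335 + 0.2668) = 0.350.

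| Four of ten | c = 100% | 90% | 75% | 50% |
|---|---|---|---|---|
| p = 20% | 12.1% | 8.8% | 5.0% | 1.3% |
| p = 30% | 35.0% | 27.3% | 16.9% | 5.0% |
| p = 40% | 61.8% | 51.3% | 35.0% | 12.1% |

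For the 20% rule, take a single look at 55 patients in an arm: 20% × 55 = 11 patients.

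| Eleven of 55 | c = 100% | 90% | 75% | 50% |
|---|---|---|---|---|
| p = 20% | 55.4% | 40.3% | 19.4% | 1.9% |
| p = 25% | 84.5% | 72.1% | 46.0% | 7.6% |

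Every row falls as c falls. If most grade 3 events are listed or in-field, c is close to 100% and the first column is nearly right.

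**The case against.** The strongest reply is that this is a drafting conflict with little practical reach. Breast radiotherapy is local treatment, and the 10.4 list together with the in-field provision should cover nearly all related grade 3 events. The fatigue example is one patient in a post-mastectomy cohort in which eleven of 12 had nodal irradiation, whereas 3.40 excludes patients with indications for comprehensive nodal irradiation. Unlisted grade 3 events are submitted, so the study team sees them. Section 16.72 lets the team suspend accrual for an unexpected profile even if the rule is not crossed, and 16.71 has the study chair and statistician, and the DSMB, review the trial at least twice a year. Deeming every grade change in a listed event related also pushes the count upwards.

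Most of this stands as to size. It does not remove the conflict. Discretionary suspension and periodic review are not substitutes for a pre-specified trigger whose input is required, and over-counting listed events does not make up for unlisted ones in any controlled way.

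Three stronger readings are tempting, and the documents do not support them:

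- *That grade 3 events can never enter the rule, or that the protocol forbids collecting their attribution.* Section 10.22 says attribution is not required; it does not bar it. Listed and in-field grade 3 events are covered, and 10.21 points towards recording relatedness.
- *That one missed event is a quarter of the four-patient trigger.* The rule counts patients. A missed event changes nothing if the same patient has another that qualifies.
- *That the adverse event analyses fail.* Sections 16.621 and 16.622 define and tabulate events regardless of attribution; relationship is an added consideration.

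**Conclusion.** The inconsistency is real and narrow. Section 10.22 conflicts with 10.21 and 16.72 for grade 3 events that are unlisted and away from the irradiated area, and the suspension rule may miss them. A second, smaller gap is that nothing says how a listed event deemed related maps to the attribution categories that 16.72 uses.

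The documents do not give the number of affected events, and it is probably small. The probabilities in the working rest on assumed values of p and c and show direction, not an expected loss. The primary endpoint in 16.21 has no attribution condition and is unaffected. The text is wrong as written and should be corrected, because the affected item is a safety trigger and the correction is cheap.

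**What to change.** Amend the first sentence of 10.22 so that all grade 3, 4 and 5 adverse events require an attribution. Keep the provision that listed events are deemed related, and state that such events count as at least possible when 16.72 is applied. This brings 10.22 into line with 16.72 and removes the conflict with 10.21 at the grades that matter for the rule. No threshold changes.

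The new field would not supply relationship for grade 1 and 2 events. If 16.621 and 16.622 are meant to consider relationship at those grades too, they should say where that information comes from.

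The cost is one attribution field for grade 3 events already submitted under 10.52, and a minor amendment.
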